15.3. Types of Data

Data for this trial will include clinical, safety, and outcome measures (e.g., clinical laboratory values, reactogenicity, and immunogenicity data).

15.4. Timing/Reports

Clinical, safety, reactogenicity and immunogenicity data will be analyzed once the last subject and last infant born to a pregnant subject completes the final visit. Analyses will occur after all data have been entered, cleaned, and monitored, and the database locked. These analyses will be made available to the sponsor for planning subsequent trials and to the clinical investigators for publication. These analyses will not be used to make any decisions concerning the conduct of this trial.

The clinical study report (CSR) will be completed when all primary safety endpoint data and all primary immunogenicity endpoint data are available. Any available data from the secondary and exploratory immunogenicity endpoints may also be included. The CSR will be amended as additional secondary and exploratory immunogenicity endpoint data become available.

Interim statistical reports may be generated as deemed necessary and appropriate by DMID. Safety and immunogenicity summary reports may be generated for the DSMB.

Cumulative safety information, study status, and primary endpoint results may be presented at a public forum in a blinded manner or presented as summaries aggregated by study arm at the discretion of the sponsor while the primary study is ongoing. While the primary study is ongoing no data will be released that is unblinding at an individual subject level, and caution will be taken to ensure that data summarized by treatment arm does not identify the treatment assignment of any individual subject. Any ad-hoc analyses, jointly developed by the SDCC and/or University of Maryland, will be executed by the SDCC as needed. Publication of manuscripts may occur at the discretion of the sponsor in accordance with DMID's Expanded Distribution of Clinical Research Endpoint Data Policy.

15.5. Study Records Retention

Study documents will be retained for a minimum of 2 years after the last approval of a marketing application in an ICH region and until there are no pending or contemplated marketing applications in an ICH region or at least 2 years have elapsed since the formal discontinuation of clinical development of the investigational product. These documents will be retained for a longer period, however, if required by local regulations. No records will be destroyed without the written consent of the sponsor. It is the responsibility of the sponsor to inform the investigator when these documents no longer need to be retained.

The participating VTEU site must contact DMID for authorization prior to the destruction of any study records. Informed consent forms that include future use sections will be maintained as long as the sample exists.

15.6. Protocol Deviations

A protocol deviation is any noncompliance with the clinical trial protocol, GCP, or protocol-specific MOP requirements. The noncompliance may be either on the part of the subject, the site

principal investigator, or other study personnel. As a result of deviations, corrective actions are to be developed by the site and implemented promptly.

These practices are consistent with the following sections of ICH E6- 4.5: Compliance with Protocol, Sections 4.5.1, 4.5.2, and 4.5.3; 5.1: Quality Assurance and Quality Control, Section 5.1.1; 5.20: Noncompliance, Sections 5.20.1, and 5.20.2.

It is the responsibility of the site principal investigator and other trial personnel to use continuous vigilance to identify and report deviations within five working days of identification of the protocol deviation, or within five working days of the scheduled protocol-required activity. All deviations will be promptly reported to DMID, via the DCC's Advantage eClinical.

All protocol deviations, as defined above, will be addressed in study subject data collection forms. A completed copy of the DMID Protocol Deviation Form will be maintained in the Regulatory File as well as in the subject's chart. Protocol deviations will be sent to the local IRB/IEC per its guidelines. The site principal investigator and other study personnel are responsible for knowing and adhering to their IRB requirements.

16. PUBLICATION POLICY

All investigators funded by the NIH must submit or have submitted for them to the National Library of Medicine's PubMed Central (<http://www.ncbi.nlm.nih.gov/pmc/>) an electronic version of their final, peer-reviewed manuscripts upon acceptance for publication, to be made publicly available no later than 12 months after the official date of publication. The NIH Public Access Policy ensures the public has access to the published results of NIH-funded research. It requires investigators to submit final peer-reviewed journal manuscripts that arise from NIH funds to the digital archive PubMed Central upon acceptance for publication. Further, the policy stipulates that these papers must be accessible to the public on PubMed Central no later than 12 months after publication.

Refer to:

- NIH Public Access Policy, <http://publicaccess.nih.gov/>
- NIH Office of Extramural Research (OER) Grants and Funding, <http://grants.nih.gov/grants/oer.htm>

As of January 2018, all clinical trials supported by the NIH must be registered on ClinicalTrials.gov, no later than 21 days after the enrollment of the first subject. Results of all clinical trials supported by the NIH, generally, need to be submitted no later than 12 months following the primary completion date. A delay of up to 2 years is available for trials that meet certain criteria and have applied for certification of delayed posting.

As part of the result posting a copy of this protocol (and its amendments) and a copy of the Statistical Analysis Plan will be posted on ClinicalTrials.gov.

For this trial the responsible party is DMID which will register the trial and post results.

The responsible party does not plan to request certification of delayed posting.

Refer to:

- Public Law 110-85, Section 801, Clinical Trial Databases
- 42CFR11
- NIH NOT-OD-16-149

Appendix A

Study Visit Type	Recruitment	Screening	Enrollment/ Vaccination	Clinic or Home Visit	Clinic or Home Visit	Follow-up	Follow-up	Follow-up	Early Termination	Unscheduled		
Study Visit Number	R-	VOO	V01	V02	V03	V04	V05	V06	V07	V08		
Study Day	1 st & 2 nd Trimesters	-30 to 1	D1	D4±1	D8±3d	D31±4d	Birth	Birth + 3d	Birth + 42d±5d	Birth + 70d±5d or 130d±5d	Birth + 180d±7d	
EGA or Infant Age	10-26 weeks	14-26 weeks	14-26 weeks	15-27 weeks	15-27 weeks	19-31 weeks						
Introduction to Study, Recruiting	X	X ^m	X ^m									
Obtain Informed Consent [∞]		X	X ^{m-1}									
Review Eligibility Criteria		X	X ^{m-1}			X ⁻¹						
Medical History [@]		X	X ^{m-1}	X ⁻¹	X ⁻¹	X ⁻¹	X ⁻¹	X ⁻¹	X ⁻¹	X ⁻¹	X ⁻¹	
Concomitant Medications [@]		X	X ^{m-1}	X ⁻¹	X ⁻¹	X ⁻¹	X ¹	X ¹	X ¹	X ¹	X ¹	
Vaccination History [@]		X	X ^{m-1}	X ⁻¹	X ⁻¹	X ⁻¹	X ¹					
Vital Signs ^S (Oral Temperature ^{°C} , Pulse, and BP)		X	X [†]			X	X				X	X
Height and Weight		X	X ^m									
Targeted Physical Exam { ¹ }		X	X ^{m-1,†#}			X	X	X	X	X	X	X
Ultrasound to Date Pregnancy		X										
Venous Blood Collection from Mother (30 mL)			X [†]			X	X			X		
Cord Blood (up to 30 mL)							X					
Venous Blood from Infant (5 mL)							X ^{&}	X	X	X		
Obtain Breastmilk Sample from Mother (10-20 mL)							X ^ψ	X	X	X		
Pre-Administration Solicited Event Assessments			X [†]									
Randomize and Vaccinate Mother			X									
30-minute Evaluation After Study Vaccination			X									

Study Visit Type	Recruitment	Screening	Enrollment/ Vaccination	Clinic or Home Visit	Clinic or Home Visit	Follow-up	Follow-up	Follow-up	Follow-up	Early Termination	Unscheduled
Study Visit Number	R [~]	VOO	V01	V02	V03	V04	V05	V06	V07	V08	
Study Day	1 st & 2 nd Trimesters	-30 to 1	D1	D4±1	D8±3d	D31±4d	Birth	Birth + 3d	Birth + 7d±5d or 130d±5d	Birth + 180d±7d	
EGA or Infant Age	10-26 weeks	14-26 weeks	14-26 weeks	15-27 weeks	15-27 weeks	19-31 weeks					
Subject AE instruction			X								
Examine Study Vaccination Site			X		X					X [†]	X ^{ml}
Post-Administration Solicited Event Assessments			X	X	X					X ^x	X ^x
Record Mother AEs and SAEs			X [/]	X	X	X	X*	X*	X*	X*	X*
Record Infant AEs and SAEs ⁺							X	X	X	X	X
Record Birth Outcomes							X	X	X	X	X
Infant Vital Signs, Head Circumference, Length, and Weight							X ^v	X ^Ω	X ^Ω	X ^Ω	X ^Ω
Infant Targeted Physical Exam, if indicated							X	X	X	X	X

[~]Recruitment and screening visits are not entered into Advantage eClinical.

^{oo}Prior to study procedures. In Mali, a research ID card with photo may be given to subjects.

[&]Venous blood for infant within 72 hrs. of birth only if no cord blood obtained.

^{ml}If not obtained in previous visit.

[†]Prior to study vaccination.

⁻Review/confirm information or activity in subjects previously consented and screened/enrolled. This includes review of the pregnant woman's medical chart to obtain information about this pregnancy that may be relevant to the conduct of this study.

[^]Review results of all clinical screening or safety laboratory evaluations.

[@]Complete medical history, medication use, and vaccination history by medical record review and interview of subjects to be obtained prior to study vaccination (screening or Day 1) and interim medical history, medication use, and vaccination history by interview of subjects to be obtained at follow-up visits.

[†]All current medications and vaccinations taken within 90 days prior to vaccination will be reviewed, but only those taken within 30 days prior to vaccination and through discharge after delivery for pregnant women will be recorded in Advantage eClinical.

[%]Subjects must not eat or drink anything hot or cold, or smoke within 10 minutes prior to taking oral temperature.

[/]If AE or SAE occurs post-vaccination.

{ Targeted physical examination, if indicated based on review of complete or interim medical history. An examination performed by a pregnant woman's own obstetrical clinician may also provide data when a targeted exam is called for. An exam should be performed for both the mother and infant if indicated for pregnant women on and after birth.

^{\$}Vital signs assessed on Day 1 (Visit 01) prior to the study vaccination will be considered as baseline and used to determine eligibility. For the birth visit, vital signs recorded for the mother as part of her delivery record may be used in lieu of study personnel performing vital sign measurements.

[#]A physical examination performed as part of routine antenatal care or a study-specific brief exam may be used.

[!]If within 30 days post vaccination.

^{*} If within 8 days post vaccination.

^{*}SAEs and new-chronic onset medical conditions only after Day 31 or delivery, whichever occurs earlier.

⁺Only medically attended AEs will be recorded.

[¶] The first colostrum collection may occur within the first 4 days of life of the infant.

[°] Infant vital signs will include axillary temperature, heart rate, and respiratory rate.

[¶] If not performed as routine care, these measurements, except for weight, may be taken by qualified members of the research team within 7 days of infant life. Weights will only be recorded when obtained at birth.

[~] Procedures will be performed on both mother and infant.

[¶] Only infant height, weight, and head circumference will be recorded at these visits.

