3.2. Study Outcome Measures

3.2.1. Primary

Safety and Tolerability:

- Safety in pregnant women: Frequency and severity of study vaccine-related serious adverse events (SAEs), and all SAEs in pregnant women from study vaccination through 6 months postpartum, description and comparison between those receiving BOOSTRIX and Td.
- Safety in pregnant women and fetuses/infants: Frequency and severity of adverse events specific to pregnancy, in pregnant women and their infants (as delineated in [Section 9.2.4](#)), description and comparison between those receiving BOOSTRIX and Td.
- Tolerability in pregnant women: Frequency and severity of solicited injection site and systemic reactogenicity events from study vaccination until 7 days following vaccination (Day 8).
- Tolerability in pregnant women: Frequency and severity of all unsolicited non-serious AEs from day of study vaccination to Day 31, description and comparison between those receiving BOOSTRIX and Td.

- Safety in the infants: Frequency and severity of study vaccine-related serious adverse events, and all SAEs in infants from birth through 6 months of age, description and comparison between infants born to women vaccinated with BOOSTRIX and Td.

Immunogenicity:

- Infant humoral immunity: Geometric Mean Concentration (GMC) of serum IgG antibodies to PT as measured by Enzyme-Linked Immunosorbent Assay (ELISA) at birth between infants born to women vaccinated with BOOSTRIX and Td.

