9. ASSESSMENT OF SAFETY

9.1. Specification of Safety Parameters

Safety will be assessed by the frequency and severity of the following:

- 1) Study vaccine-related Serious Adverse Events occurring from the time of the study vaccination through the visit 6 months postpartum (180 days of life for the infant visit) for pregnant subjects and infants. All SAEs during this timeframe will be assessed and documented.
- 2) Adverse Events related to pregnancy and the infant as delineated below in [Section 9.2.4](#). For the pregnant woman/mother: pregnancy loss, vaginal bleeding (antepartum or postpartum), post-abortal endometritis/salpingitis, preterm rupture of membranes, preterm contractions/labor/delivery, poor fetal growth, hypertension/pre-eclampsia/eclampsia, chorioamnionitis, postpartum endometritis, gestational diabetes mellitus. For the infant: preterm birth, low birth weight, neonatal complications, and congenital anomalies.
- 3) Solicited Adverse Events – reactogenicity events occurring from the time of study vaccination through 7 days after study vaccination (Day 8) or until resolution.
 - a. Injection site reactions including ecchymosis (bruising), erythema (redness), induration (hardness)/edema(swelling), pain, and tenderness.
 - b. Systemic reactions including fever (days 4 and 8 only during home visits), feverishness (chills/shivering/sweating), fatigue (tiredness), malaise (general unwell feeling), myalgia (body aches/muscular pain exclusive of the injection site), arthralgia (joint pain exclusive of the injection site), headache, nausea, and allergic reaction (pruritus/urticaria).
- 4) Unsolicited Non-Serious Adverse Events – all non-serious unsolicited adverse events will be assessed and documented, and all study vaccine-related non-serious adverse events occurring from the time of study vaccination through approximately 30 days after study vaccination (the Day 31 visit). For pregnant women who deliver before Day 31, unsolicited adverse events will be recorded until delivery.
- 5) Major Congenital Anomalies

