9.2.4. Grading of Specific Adverse Events in the Pregnant Women and their Infants

Table 8: Maternal and Infant Adverse Events

Maternal Adverse Events (Adverse Events during Pregnancy)				
Parameter	Normal	Grade 1	Grade 2	Grade 3
Pregnancy loss (Pregnancy does not result in a live birth)	None	N/A	N/A	Spontaneous abortion or miscarriage
Spontaneous abortion or miscarriage in the first or second trimester of gestation				
Fetal death at or after 20 weeks of gestation (stillbirth)				
Bleeding (vaginal) during pregnancy prior to the onset of labor	None	Spotting or bleeding less than menses	Bleeding like menses or heavier, no intervention indicated	Profuse bleeding with dizziness or orthostatic hypotension, transfusion indicated
Postpartum hemorrhage	EBL ^c ≤500 cc for vaginal delivery or ≤1000 cc after CS or reported as normal	EBL 501-1000 for vaginal delivery or 1001-1500 for CS or reported as slightly increased	EBL >1000 for vaginal delivery or >1500 for CS, with or without mild dizziness, no transfusion required	Hemorrhage at a level for which transfusion of packed cells or any amount of other blood components is indicated
Postabortal endometritis/salpingitis	None	Low grade fever and uterine tenderness, resolved with oral antibiotics	Moderate symptoms, requiring ≤3 days of parenteral antibiotics	Severe symptoms requiring >3 days of IV antibiotics or development of TOA
Preterm rupture of membranes	None	N/A	Preterm rupture but not resulting in delivery before 37 weeks gestation	Preterm rupture resulting in delivery before 37 weeks gestation

Preterm contractions /labor/delivery^e	None Braxton Hicks contractions (as early as second trimester)	Preterm contractions which resolve without medical intervention	Preterm contractions with cervical change which result in medical intervention but not resulting in preterm delivery	Delivery before 37 weeks gestation
Poor fetal growth If infant is small for gestational age on newborn exam: report as NEONATAL OUTCOME based on birth weight (see below)	At or above 10 th percentile	Fetal growth <10 th percentile but ≥3 rd percentile for gestational age by ultrasound	N/A	Fetal growth <3 rd percentile for gestational age by ultrasound
Hypertension, preeclampsia/eclampsia	None	Pregnancy induced hypertension	Preeclampsia	HELLP syndrome, or eclampsia,

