Chorioamnionitis	None	Fever (38°C–38.4°C or 100.4°F–100.9°F) with two or more: FHR ^e >160 BPM ^f , maternal HR >120, uterine tenderness between contractions or purulent AF or preterm labor	Same as Grade 1 plus fever 38.5°C–40°C or 101°F–104°F	Criteria for Grade 2 plus fetal distress or fever >40°C or 104°F
Postpartum endometritis	None	Low grade fever and uterine tenderness, resolved with oral antibiotics	Moderate symptoms, treated by ≤3 days of parenteral antibiotics	Severe symptoms treated with >3 days of IV antibiotics, addition of heparin, or operative intervention
Gestational diabetes mellitus	N/A	New onset controlled by diet	New onset with initiation of medical therapy	Uncontrolled despite treatment modification
Clinical AE, pregnancy-related, NOT identified elsewhere in this AE Grading Table	None	Symptoms causing no or minimal interference with usual social & functional activities	Symptoms causing greater than minimal interference with usual social & functional activities	Symptoms causing inability to perform usual social & functional activities

Mode of delivery^f (normal spontaneous vaginal delivery, induced delivery, assisted vaginal delivery, Caesarean Section)	Not reported as AE/SAE. Mode of delivery is a procedure and should not be reported or graded as an AE/SAE. The reason for selecting the mode of delivery (for example: Caesarean Section for severe preeclampsia) should be reported and graded as appropriate.
--	---

**Infant Adverse Events
(Neonatal and Infant Events)**

Parameter	Normal	Grade 1	Grade 2	Grade 3
Preterm birth^g	Born after 36 6/7 weeks gestation	Late preterm: 34 to 36 6/7 weeks gestation	Early preterm: 32 to 33 6/7 weeks gestation	Very or extremely preterm: ≤ 31 6/7 weeks gestation
Birth weight (grams)^g (Small, appropriate, large for gestational age)	Birth weight ≥2500		Low birth weight: 1501-2500	Very low birth weight ≤1500
Report separately poor fetal growth (as above)				
Neonatal complications in a term infant	Normal term infant discharged home with mother after uncomplicated delivery and nursery course	Transient signs and symptoms requiring no interventionⁱ , and resolved spontaneously ^h	Signs/symptoms requiring interventionⁱ but discharged home with mother (± 2 days) , or close to it	Required NICU for more than 1 week, and/or interventions (including surgery) leading to prolonged hospitalization (report SAE) ^j

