9.4. Type and Duration of Follow-up of Subjects after Adverse Events

Non-serious AEs will be collected, assessed, and followed through resolution from the time of study vaccination through approximately 30 days after study vaccination. For pregnant women, this period extends from vaccination until Day 31 or delivery, whichever occurs earlier. All unresolved non-serious AEs will be followed through resolution even if this extends beyond the study-reporting period.

SAEs and new-onset chronic medical conditions will be collected, assessed, and followed from the time of study vaccination through resolution even if this extends beyond the study-reporting period. The reporting period extends from vaccination until 6 months postpartum (180 days of life for the infant visit) for pregnant women.

Resolution of an AE/SAE is defined as the return to pretreatment status or stabilization of the condition with the expectation that it will remain chronic.

Follow-up procedures, evaluations, and outcomes will be recorded on the appropriate data collection form.

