#### **9.5. Pregnancies**

Every attempt was made to follow subjects to completion of pregnancy to document the outcome, including information regarding any complications with pregnancy and/or delivery. A table summarizing the total pregnancies, number of live births, and number of spontaneous abortions, elective abortions or still births by treatment group will be presented ([Table 75](#)). In addition, a listing of pregnancies and outcomes will be presented ([Listing 18](#), [Listing 19](#), [Listing 20](#), and [Listing 21](#)). A summary of infant size for gestational age at birth by treatment group will be presented in [Table 76](#) and [Figure 233](#).

Pregnancy related adverse events will be collected throughout the study and graded on a scale of 0 (absent), 1 (mild), 2 (moderate) and 3 (severe). Pregnancy related maternal events include pregnancy loss, bleeding during pregnancy or labor, postpartum hemorrhage, postabortal endometritis/salpingitis, preterm rupture of membranes, preterm contractions/labor/delivery, poor fetal growth, hypertension/preeclampsia/eclampsia, chorioamnionitis, postpartum endometritis, gestational diabetes and other pregnancy related AE. Infant events include preterm birth, birth weight, neonatal complications in a term infant, other AE in newborn and congenital abnormality/birth defect ([Table 8](#)).

The proportion of subjects reporting at least one pregnancy related adverse event will be summarized for each pregnancy related adverse event, any maternal symptom, and any infant symptom. The 95% CI will be calculated using Clopper-Pearson methodology from a binomial distribution (SAS Proc Freq with a binomial

(exact) option) will be presented ([Table 77](#) and [Table 78](#)). A Fisher's exact test w the difference in the proportion of subjects reporting a pregnancy related adverse event ([Table 79](#) and [Table 80](#)).

For each pregnancy related event, any maternal event, and any infant event, the maximum severity will be summarized for the maternal and infant Safety populations. The number and percentage of subjects reporting each event will be summarized by the maximum severity and treatment group. ([Table 81](#) and [Table 82](#)). The frequency of pregnancy- and infancy-related adverse events are presented in a bar chart in [Figure 229](#) and [Figure 231](#). The incidence of pregnancy- and infancy-related AEs are presented in [Figure 230](#) and [Figure 232](#).

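### Non-serious pregnancy-related events in the mother have two conflicting recording windows: to Day 31 or delivery in Protocol 9.4 and Appendix A, but the whole study in SAP 9.5

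*Protocol*

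**What the plan says.** Protocol 3.2.1 makes this a primary safety outcome: "Frequency and severity of adverse events specific to pregnancy, in pregnant women and their infants", described and compared between arms. No recording window is attached, and SAP 3.2.1 is the same.

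Two rules then bear on when these events are recorded in the mother.

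- **Short window.** Protocol 9.4, on non-serious adverse events in general, says: "For pregnant women, this period extends from vaccination until Day 31 or delivery, whichever occurs earlier". In Appendix A, the row for recording maternal events carries an asterisk from the delivery visit (V05) on. Its footnote reads "SAEs and new-chronic onset medical conditions only after Day 31 or delivery, whichever occurs earlier", and SAP Table 2 repeats it.
- **Long window.** SAP 9.5 says: "Pregnancy related adverse events will be collected throughout the study and graded", on a 0 to 3 scale.

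Protocol 9.1 lists pregnancy and infant events as item 2, including "vaginal bleeding (antepartum or postpartum), post-abortal endometritis/salpingitis", with no time limit. Protocol 9.3 gives windows for maternal solicited events, maternal unsolicited non-serious events, maternal serious events and infant events, but none for maternal Section 9.2.4 events.

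**The concern.** A site cannot follow both rules. Under the short window, a non-serious Table 8 event in the mother after the cutoff is not entered as an adverse event. The analysis described in SAP 9.5 would nevertheless treat the data as if they covered the whole study.

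The SAP's denominator makes this matter. SAP 9.3 divides by the full size of the population analysed, and Tables 77, 79 and 81 take the Maternal Safety Population. A woman whose event was outside the recording rule is therefore counted as having none. A row for events that nobody was told to record would look like evidence of absence, with an exact confidence interval attached.

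**Working it through.** The plan gives no figure of its own on this point. The check is a comparison of texts, with some day arithmetic.

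**1. Does another passage settle the conflict?**

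- Protocol 9.4 and the footnote make no exception for Section 9.2.4 events.
- At V05 (Protocol 7.4.2.2.1), the 30-day condition on non-serious events has unbalanced parentheses and can be read in more than one way.
- V06 to V08 ask for new congenital anomalies and serious events. They neither ask for other maternal events nor expressly exclude them.
- SAP 9.3.2 lists Tables 77 and 78 among its summaries of unsolicited events. SAP Table 45, and Listing 13 as against Listing 12, keep the pregnancy-related events separate.

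None of these passages resolves it.

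**2. Where does the cutoff fall?** Vaccination is allowed from 14 0/7 to 26 6/7 weeks (Protocol 5.1), and Day 31 is vaccination + 30 days, with a visit window of ±4 days.

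- Earliest: 14 × 7 + 30 = 128 days = 18 2/7 weeks.
- Latest: 26 × 7 + 6 + 30 = 218 days = 31 1/7 weeks; with +4 days, 222 days = 31 5/7 weeks.

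For scale only, assume delivery at 37 0/7 to 40 0/7 weeks (259 to 280 days; not in the documents). The 30 days then cover 30/182 = 16.5% to 30/161 = 18.6% of the time from vaccination to delivery for the earliest vaccination. For the latest they cover 30/92 = 32.6% to 30/71 = 42.3%. No postpartum time is covered. These are shares of time, not of events.

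**3. Which Table 8 events does the cutoff contradict?**

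- Postpartum hemorrhage is graded from Grade 1: "EBL 501-1000 for vaginal delivery or 1001-1500 for CS or reported as slightly increased".
- Postpartum endometritis is graded from Grade 1: "Low grade fever and uterine tenderness, resolved with oral antibiotics". Both follow delivery, so both always fall after the cutoff.
- Table 8 footnote e asks for a preterm delivery to be reported as an event in the mother as well as in the infant. Day 31 falls no later than 31 1/7 weeks (31 5/7 with the visit window), so any preterm delivery from then up to 36 6/7 weeks comes after it.

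The protocol's own event list therefore does not fit its cutoff.

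**4. What would the tables show?** For Table 77, SAP 9.5 states: "The 95% CI will be calculated using Clopper-Pearson methodology from a binomial distribution". With 0 events in n women, the upper limit is 1 − 0.025^(1/n). Take the planned arm sizes, assume all are vaccinated, and assume no serious case:

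- BOOSTRIX, n = 133: 1 − 0.025^(1/133) = 0.0274, so 0/133 (0-2.7%).
- Td, n = 67: 1 − 0.025^(1/67) = 0.0536, so 0/67 (0-5.4%).

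The two postpartum rows would show these limits whatever the true number of non-serious cases.

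**5. What is still collected after the cutoff?**

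- Maternal serious events, which include any event causing or prolonging hospitalization (Protocol 9.2.5), and new-onset chronic conditions.
- Birth outcomes at V05 to V08, and medically attended infant events to day 180. Pregnancy loss and preterm delivery are therefore largely recoverable.
- Blood pressure at V05, graded in Protocol 9.2.3 and tabulated at delivery under SAP 9.7, so hypertension is partly recoverable.

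Poor fetal growth is not recoverable in this way. Table 8 defines it by ultrasound and sends a small newborn to a separate neonatal outcome, so infant size at birth does not fill that maternal row.

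**The case against.** The strongest defence is that the general limit was never meant for Table 8 events. Protocol 9.1 lists them in item 2 and puts the Day 31 limit in item 4, on unsolicited non-serious events. Protocol 9.3 limits that same class. Footnote e directs a maternal report that will often fall after Day 31. On this reading, SAP 9.5 simply states the window for a separate class of event.

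That is a fair account of likely intent, but it does not remove the conflict. Protocol 9.4 speaks of non-serious events without exception, the footnote covers the whole maternal row, and no protocol passage states a longer window. SAP 9.3.2 also places the pregnancy-related tables under unsolicited events.

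The defence does limit the claimed loss. A reader might infer that non-serious postpartum events can never be captured at all. The documents do not go that far. SAP 9.5 also describes follow-up of pregnancy outcomes, including complications of pregnancy and delivery. Protocol 7.4 permits chart review at any time, and Protocol 6.6 records maternal medications through discharge after delivery. Some cases may surface by these routes. They are not systematic, however: chart review is optional, and none of these routes instructs the site to enter and grade a Table 8 event.

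**Conclusion.** The contradiction stands, between protocol and SAP and also within each: SAP 9.5 against SAP Table 2, and Protocol Table 8 against Protocol 9.4. It should be fixed.

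Its effect is under-counting of non-serious maternal events after the cutoff, and lower sensitivity of the maternal part of a primary safety endpoint. The clearest case is the two postpartum rows in step 4. Those figures rest on a literal reading of Protocol 9.4 and the footnote, the planned arm sizes and no serious case. The Manual of Procedures and the eCRF, which would show which rule sites were told to apply, are not among the documents.

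Two stronger conclusions might be inferred and are not supported. First, the BOOSTRIX-Td comparison is not shown to be biased: the rule is identical in both arms of a double-blind trial. Secondly, no number of lost events can be stated, because the documents give no event rates by period. The infant tables (78, 80 and 82) are unaffected, and no sample size or significance level depends on the point.

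**What to change.** State one recording window for maternal Section 9.2.4 events and use it in Protocol 9.1, 9.3 and 9.4, the V05 to V08 visit text, the Appendix A footnote, SAP 9.5 and SAP Table 2, with a matching eCRF instruction. For example: maternal Table 8 events of any grade are recorded from study vaccination through V08; other unsolicited non-serious maternal events are recorded to Day 31 or delivery, whichever comes first.

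If the sponsor prefers the short window, correct SAP 9.5, label Tables 77, 79 and 81 with the window actually used, and show the postpartum hemorrhage and postpartum endometritis rows as serious events only.

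The cost is a text clarification and slightly more data entry. No new visit or procedure is needed, because V05 to V08 already take an interim history from the mother.
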